8.4 Early Termination/Discontinuation

If a subject is discontinued from the trial prior to Visit 3, then all safety evaluations that are to be performed at Visit 3 should be performed on the day of discontinuation (early termination) or at the discretion of the investigator.

Adverse events (both elicited and observed) and serious adverse events will be monitored throughout the trial. The investigator will promptly review all adverse events (both elicited and observed) for accuracy and completeness. All adverse events will be documented on the appropriate source document and case report form.

If a positive pregnancy test is observed during the trial, the investigator will notify [REDACTED] immediately. The investigator shall request from the subject and/or the subject's physician copies of all related medical reports during the pregnancy and shall document the outcome of the pregnancy. The investigator will retain the reports together with the subject's source documents and will provide a copy of all documentation to [REDACTED]. Pregnant subjects will be discontinued from the trial as per the exclusion criteria.

8.5 Schedule of Visits, Measurements, and Dosing

8.5.1 Scheduled Visits

Appendix 1 details the schedule of visits and measurements.

8.5.2 Unscheduled Visits

Unscheduled visits may be performed in order to ensure subject safety. All procedures performed at an unscheduled visit will be recorded in the source documents and on the Unscheduled Visit eCRF pages. Any procedure indicated in the eCRF that is not performed should be indicated as "Not done."

Evaluations that may be conducted at an unscheduled visit include:

- Slit lamp examination;
- Visual acuity;
- Intraocular pressure;
- Urine pregnancy test;
- Assessment of adverse events;
- Assessment of concurrent medications and/or treatments; and
- Any other assessments needed in the judgment of the investigator.

8.6 Subject Disposition

8.6.1 Completed Subjects

A completed subject is one who has not been discontinued from the trial and has completed all applicable assessments.

8.6.2 Discontinued Subjects

Subjects may be discontinued prior to the completion of the trial for reason, which may include:

- Adverse events,
- Protocol violations,
- Administrative reasons (e.g., inability to continue), or
- Sponsor termination of the trial.

Notification of subject discontinuations and reasons for discontinuation will be made to [REDACTED] and will be clearly documented on the source document.

8.7 Study Duration

Participation in the clinical trial is estimated to be approximately 2 weeks per subject.

8.8 Monitoring and Quality Assurance

During the course of the trial, a monitor, or designee, will make routine site visits to review protocol compliance; assess test article accountability, storage conditions, and subject safety; and ensure the trial is being conducted

according to the pertinent regulatory requirements. Review of medical records will be performed in a manner that adequately maintains subject confidentiality. Further details of the study monitoring will be outlined in a monitoring plan.

█ quality assurance and or its designees may carry out on-site inspections and audits, which may include source data checks. Therefore, direct access to the original source data will be required for inspections and audits. All inspections and audits will be carried out with consideration of data protection as well as subject confidentiality to the extent that local, state, and federal laws apply.

9 ADVERSE EVENTS

9.1 Adverse Event

For the purposes of the trial, an adverse event is defined as any untoward medical event occurring after signing of the informed consent until exited from the trial. An adverse event can therefore be any unfavorable and unintended sign, symptom, or disease occurring after the subject started the clinical trial, without any judgment about causality. Any pre-existing medical condition that worsens during the trial will also be considered a new adverse event. Documentation regarding the adverse event should be made as to the nature, date of onset, end date, severity, relationship to study procedure, expectedness, action(s) taken, seriousness, and outcome of any sign or symptom observed by the investigator or reported by the patient upon indirect questioning.

9.1.1 Severity

Severity of an adverse event is defined as a qualitative assessment of the degree of intensity of an adverse event as determined by the investigator or reported by the subject. Severity assessments will be made irrespective of relationship to study procedures or seriousness of the event and will be characterized according to the following definitions:

- █
- █
- █
- █

9.1.2 Relationship to Study Procedures

The relationship of each adverse event to the study procedures should be determined by the investigator using the definitions below. Decisive

factors for the assessment of causal relationship of an adverse event to the study procedures include, but are not limited to, temporal relationship between the adverse event and the procedure, known side effects of the procedure medical history, and/or concomitant medication:

- *Definite*: When there are good reason and sufficient documentation to demonstrate a direct causal relationship between study procedure and adverse event;
- *Probable*: When there are good reasons and sufficient documentation to assume a causal relationship in the sense of plausible, conceivable, or likely, but not necessarily highly probable.
- *Possible*: When there is sufficient information to accept the possibility of a causal relationship in the sense of not impossible and not unlikely, although the connection is uncertain or doubtful (e.g., missing data or insufficient evidence).
- *None*: When there is sufficient information to accept a lack of a causal relationship, in the sense of impossible and improbable.
- *Unclassified*: When the causal relationship is not assessable for whatever reason due to insufficient evidence, conflicting data, or poor documentation.

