9.1.3 Expectedness

The expectedness of an adverse event should be determined based upon existing safety information about the study procedures. Therefore, the following definition will be used:

- *Unexpected*: An adverse event that is not listed in the safety information available for the study procedure at the specificity or severity that has been observed.
- *Expected*: An adverse event that is listed in the safety information available for the study procedure at the specificity and severity that has been observed.
- *Not Applicable*: Any adverse event that is unrelated to the study procedure.

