9.3.1 Reporting a Suspected Unexpected Adverse Reaction

All adverse events that are related (definite, probable, possible) and unexpected are to be reported to [REDACTED] and the IRB, as required by the IRB; federal, state, or local regulations; and governing health authorities.

[figure not shown]

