9.3.2 Reporting a Serious Adverse Event

To ensure subject safety, all serious adverse events, regardless of relationship to the test article, must be immediately reported. All information relevant to the serious adverse event must be recorded on the appropriate source

documents. The investigator is obligated to pursue and obtain information requested by [REDACTED] in addition to that information reported on the source document. All subjects experiencing a serious adverse event must be followed up and the outcome reported.

In the event of a serious adverse event, the investigator must notify [REDACTED] immediately; obtain and maintain all pertinent medical records, information, and medical judgments from colleagues who assisted in the treatment and follow-up of the subject; provide [REDACTED] with a complete case history; and inform the IRB of the adverse event within their guidelines for reporting serious adverse events.

Contact information for reporting serious adverse events:

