17.1 Adverse Events

An adverse event is defined as any untoward medical occurrence associated with the use of an test article in humans, whether or not considered test-article-related. An adverse event can be any unfavorable and unintended sign (e.g., an abnormal laboratory finding), symptom, or disease temporally associated with the use of test article, without any judgment about causality. Exacerbation of conditions related to the signs and symptoms of dry eye disease will not be reported as an adverse event. The adverse event reporting period ends upon trial exit. Study drug includes the investigational drug under evaluation.

All adverse events will be coded using MedDRA Version 27.0 (or higher).

Treatment-emergent adverse events (TEAEs) are defined as any adverse event that occurs or worsens on or after the first dose of study treatment. Adverse events recorded in the eCRF which began prior to treatment will not be included in the summary tables but will be included in the adverse event data listings.

An overall summary will be presented that includes the number and percentage of subjects who experienced at least one AEs, ocular AEs, non-ocular AEs, SAEs, AEs by maximal severity, AEs by relationship to study procedure, AEs leading to treatment discontinuation, and AEs resulting in death by treatment arm for the Safety Population. In addition, overall TEAEs and the number and percentage of subjects who experienced at least one TEAE, ocular TEAEs, non-ocular TEAEs, TE-SAEs, TEAEs by maximal severity, TEAEs by relationship to study procedure, TEAEs leading to treatment discontinuation, and TEAEs resulting in death by treatment arm for the Safety Population.

Separate summaries will be provided for the following categories of AEs:

- Ocular AEs by SOC and PT
- Non-ocular AEs by SOC and PT

- Ocular TEAEs by SOC and PT
- Non-ocular TEAEs by SOC and PT
- Instillation Site Ocular TEAEs by Duration of Time
- Ocular TEAEs by SOC, PT, and maximal severity
- Non-ocular TEAEs by SOC, PT, and maximal severity
- Ocular TEAEs by SOC, PT, and strongest relationship to study procedure
- Non-ocular TEAEs by SOC, PT, and strongest relationship to study procedure
- Ocular TEAEs by SOC, PT, maximal severity, and strongest relationship to study procedure
- Non-ocular TEAEs by SOC, PT, maximal severity, and strongest relationship to study procedure
- TEAEs That Led to Premature Treatment Discontinuation
- SAEs

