Adverse Events and TEAEs will be summarized using discrete summary statistics and presented by treatment arm and all subjects for the the Safety Population. If a subject reports the same PT multiple times within the same SOC, that PT will only be reported once within that SOC. As with the PT, if a subject reports multiple conditions within the same SOC, that SOC will only be reported once. In the summaries, SOCs will be listed in ascending alphabetical order. PTs will be listed in order of descending frequency within each SOC for all subjects.

A missing severity will be considered Severe. 'Drug Related' will be defined as 'Definitely Related', 'Probably related' or 'Possibly Related', excluding 'Unlikely Related' and 'Not Related'. A missing relationship will be considered as 'Definitely Related'.

All AEs, ocular AEs, non-ocular AEs, and SAEs will be presented in subject listings.

18. Other Safety Variables

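### Causality and expectedness of adverse events are rated only against study procedures, yet the SAP defines 'Drug Related' from that single rating

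*Protocol*

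**What the plan says.** **What is collected.** Protocol 9.1 lists what is documented for each adverse event. The relevant part reads "severity, relationship to study procedure, expectedness, action(s) taken, seriousness, and outcome", so there is one relationship item and its object is the study procedure. Protocol 9.1.2 gives the instruction, "The relationship of each adverse event to the study procedures should be determined by the investigator using the definitions below", with five categories: Definite, Probable, Possible, None and Unclassified.

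**Expectedness.** Protocol 9.1.3 states: "The expectedness of an adverse event should be determined based upon existing safety information about the study procedures". An unexpected event is one "not listed in the safety information available for the study procedure" at the specificity or severity observed. Events unrelated to the procedure are classed as Not Applicable.

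**How the ratings are used.** Protocol 9.3.1 applies them: "All adverse events that are related (definite, probable, possible) and unexpected are to be reported". SAP 17.1 tabulates by the same item, for example "Ocular TEAEs by SOC, PT, and strongest relationship to study procedure", and then adds a definition with a different object: "Drug Related' will be defined as 'Definitely Related', 'Probably related' or 'Possibly Related". It counts a missing relationship as 'Definitely Related'.

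**Where the test article appears.** Protocol 9.3.2 requires that "all serious adverse events, regardless of relationship to the test article, must be immediately reported". That mentions relationship to the test article but asks for no rating of it. The adverse event definition in SAP 17.1 does the same.

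**The concern.** The trial exposes subjects to two things that could each cause an ocular adverse event: the drops, and a chamber that SAP 5.1 describes as facilitating dry eye symptoms. A reader of the safety tables will want to know which of these the investigator held responsible. The plan collects one rating with an undefined object and then gives it two names, relationship to study procedure and 'Drug Related'.

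Two things are at stake. The first is labelling: an event blamed on the chamber or an examination would fall under 'Drug Related'. The second is the category in Protocol 9.3.1. Whether a drug-attributed event enters it depends on whether a site regards dosing as a study procedure, and two sites could answer differently.

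**Working it through.** There is no figure in the plan to reproduce and no arithmetic to do. The check is to follow one event through the rules under each possible meaning of 'study procedures'.

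**Step 1: is the term defined?** No. Protocol 8.3.1 is headed as procedures performed at the study visit, and it lists vehicle instillation (Visit 1), Doses 1 to 4 (Visit 2), test article instillation (Visit 3) and CAE exposure. That supports a broad reading that includes dosing. Against it, Protocol 9.1.2 weighs known side effects of the procedure without naming the test article, and Protocol 9.3.2 speaks of the test article as a separate object. Neither document settles the question.

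**Step 2: apply the rules.**

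| Investigator's view | Narrow reading (dosing is not a procedure) | Broad reading (dosing is a procedure) |
|---|---|---|
| Caused by the drop | Relationship None; expectedness Not Applicable; not 'Drug Related'; cannot meet 9.3.1 | Related; 'Drug Related'; meets 9.3.1 if unexpected |
| Caused by the CAE or an examination | Related; 'Drug Related'; meets 9.3.1 if unexpected | Related; 'Drug Related'; meets 9.3.1 if unexpected |
| Rating left blank | Counted as 'Definitely Related', so 'Drug Related' | The same |

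Under the narrow reading the label is the wrong way round for the first two rows. Under the broad reading those rows are identical, so the record does not show which cause the investigator had in mind.

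**Step 3: can timing supply the answer?** Partly. The four Visit 2 doses are given outside the CAE (SAP 5.1), so events then have no concurrent chamber exposure. At Visit 3 a dose is given about 5 minutes before CAE entry and another about 50 minutes after it (Protocol 7.1.3), so timing does not separate the two causes.

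**Step 4: is the reference for expectedness tied to the product?** Not in the text. The synopsis places known and potential risks in the Investigator's Brochure, and Protocol 9.1.3 does not cite it. Under the broad reading the brochure could count as safety information for the procedure, but that has to be inferred.

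**Step 5: do the scales match?** No. 'Drug Related' in SAP 17.1 excludes 'Unlikely Related', a category absent from Protocol 9.1.2, and the SAP gives no place to the protocol's Unclassified. Any new item needs one agreed scale.

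**The case against.** The strongest reply is that dosing is a study procedure in the protocol's own usage (8.3.1). Drug reactions then receive a related rating, 9.3.1 captures them, and the brochure is part of the relevant safety information. This is a fair reading and may be the intended one. It removes the missed trigger. It does not remove the combined rating.

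A reader might go further and infer that drug-caused and chamber-caused events cannot be separated at all, or that the chamber masks a drug signal. The documents do not support that:

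- The arms are randomized 1:1 with the same CAE exposure, so the comparison of TEAE rates needs no causality rating. As an illustration, assume 10% of reproxalap subjects have a drug-caused event and 5% to 20% of both arms a chamber-caused one. With no overlap the rates are 15% v 5% and 30% v 20%, a difference of 10 points each time. With independent causes they are 14.5% v 5% and 28% v 20%, differences of 9.5 and 8 points. The contrast is diluted in relative terms but is not hidden. All these rates are assumptions.
- SAP 17.1 plans a table of instillation site ocular TEAEs.
- SAP 17.1 does not report exacerbation of dry eye signs and symptoms as an adverse event, so the number of chamber-caused events may be small.

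A reader might also infer that the SAP reports drug-related tables. It defines the term, but none of the tables listed in 17.1 carries that label.

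Two further limits stand. Investigators are masked, so a second item would not give perfect attribution. The eCRF is not among the documents, so whether it already holds such an item cannot be checked.

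**Conclusion.** The point holds for investigator attribution of individual events. The protocol text provides one causality rating and one expectedness rating, both against an undefined 'study procedures', and none against the test article. SAP 17.1 gives that rating a drug label, and Protocol 9.3.1 depends on it. On the narrow reading a drug-attributed event can miss the related-and-unexpected category. On the broad reading that gap closes, but drop and chamber remain merged, chiefly at Visit 3.

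The consequence is bounded. Protocol 9.3 has all adverse events reported, Protocol 9.3.2 has serious events reported whatever their cause, and the comparison between arms and the efficacy analysis do not use the rating. No size can be given, because the documents contain no adverse event rates. The conclusion assumes that the eCRF follows the list in Protocol 9.1.

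**What to change.** - **Protocol 9.1, 9.1.2 and the eCRF:** record relationship to test article as its own item, beside relationship to study procedure (defined as the CAE and examinations), on the same scale.
- **Protocol 9.1.3:** refer expectedness of test-article-related events to the Investigator's Brochure.
- **Protocol 9.3.1:** apply the trigger when either rating is definite, probable or possible and the event is unexpected.
- **SAP 17.1:** derive 'Drug Related' from the test-article item, including the missing-value rule. Use the protocol's categories and say where Unclassified falls. Keep the procedure-relationship tables as a second set.

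The cost is one more eCRF item, if it is not already there, a few sentences in each document and a few extra tables. No additional visit, procedure or staff is needed. The item should be in place before enrolment, since attribution is best recorded when the event occurs.

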9.1.3 Expectedness

The expectedness of an adverse event should be determined based upon existing safety information about the study procedures. Therefore, the following definition will be used:

- *Unexpected*: An adverse event that is not listed in the safety information available for the study procedure at the specificity or severity that has been observed.
- *Expected*: An adverse event that is listed in the safety information available for the study procedure at the specificity and severity that has been observed.
- *Not Applicable*: Any adverse event that is unrelated to the study procedure.

9.2 Serious Adverse Events

An adverse event is considered serious if, in the view of either the investigator or Sponsor, the adverse event results in any of the following outcomes:

- Death;
- A life-threatening adverse event;
 - Note: An adverse event is considered “life-threatening” if, in the view of either the investigator or Sponsor, the occurrence of the adverse event places the subject at immediate risk of death. A life-threatening adverse event does not include an adverse event that, had it occurred in a more severe form, might have caused death.

- Inpatient hospitalization or prolongation of existing hospitalization;
 - Note: The term “inpatient hospitalization” refers to any inpatient admission (even if less than 24 hours). For chronic or long-term inpatients, inpatient admission includes transfer within the hospital to an acute/intensive care inpatient unit. Inpatient hospitalization does not include: emergency room visits, outpatient/same-day/ambulatory procedures, observation/short stay units, rehabilitation facilities, hospice facilities, nursing homes, or clinical research/Phase 1 units.
 - Note: The term “prolongation of existing hospitalization” refers to any extension of an inpatient hospitalization beyond the stay anticipated or required for the reason for the initial admission as determined by the investigator or treating physician.
- A persistent or significant incapacity or substantial disruption of the ability to conduct normal life functions;
- Note: A serious adverse event specifically related to visual threat would be interpreted as any potential ocular impairment or ocular damage (e.g., hemorrhage, retinal detachment, central corneal ulcer, or damage to the optic nerve).
- A congenital anomaly/birth defect in the fetus or child of a female subject if the subject was exposed to test article when pregnant with the fetus or child.

Important medical events that may not result in death, are life-threatening, or require hospitalization may be considered serious when, based upon appropriate medical judgment, the subject may be jeopardized or may require medical or surgical intervention to prevent one of the outcomes listed above.

9.3 Procedures for Reporting Adverse Events

All adverse events and associated outcomes must be reported to [REDACTED] and the Institutional Review Board (IRB, as required by the IRB; federal, state, or local regulations; and governing health authorities) and recorded on the appropriate source document.

9.3.1 Reporting a Suspected Unexpected Adverse Reaction

All adverse events that are related (definite, probable, possible) and unexpected are to be reported to [REDACTED] and the IRB, as required by the IRB; federal, state, or local regulations; and governing health authorities.

[figure not shown]
9.3.2 Reporting a Serious Adverse Event

To ensure subject safety, all serious adverse events, regardless of relationship to the test article, must be immediately reported. All information relevant to the serious adverse event must be recorded on the appropriate source

documents. The investigator is obligated to pursue and obtain information requested by [REDACTED] in addition to that information reported on the source document. All subjects experiencing a serious adverse event must be followed up and the outcome reported.

In the event of a serious adverse event, the investigator must notify [REDACTED] immediately; obtain and maintain all pertinent medical records, information, and medical judgments from colleagues who assisted in the treatment and follow-up of the subject; provide [REDACTED] with a complete case history; and inform the IRB of the adverse event within their guidelines for reporting serious adverse events.

Contact information for reporting serious adverse events:

